Descriptive statistics: Descriptive statistics, including percentage and means with 95% confidence intervals, will be used to quantify sample characteristics of the participating wards and participants. To investigate potential bias in characteristics due to self-selection, characteristics for participants and the source population will be compared for each participating wards. We will further quantify bias by calculating the ratio of proportions for categorical data and difference in means for continuous data. *Analytical statistics:* For investigating the effects of PASC on surgery-related complications, we will use binary logistic regression models using the control period as reference category. Correlation between outcomes on the same hospital (ICC) will be considered by including a random intercept for the hospitals

in the various models (exchangeable correlation assumed). To account for potential temporal trends in the outcome, we will include calendar month as a continuous (linear or nonlinear) term in all models. Additional adjustment would be required if selection bias is present.

Variables are gender (0/1), age (in years), comorbidity (ASA-classification 1-5), type of anesthesia (general, spinal/regional, or combination – nominal scores), type of surgery (nominal scores), length of surgery (knife-time in minutes/hours), type of hospital (nominal scores), and month of surgery (1-27). Outcome variables: complication (one or more) up to 30 days after surgery, readmission to hospital within 30 days, mortality up to 30 days after surgery, and length of hospital stay.

Non-response and selection bias

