Harris et al. Development and validation of patients' surgical safety checklist. BMC Health Services Research. 2022; 22:259.

Kline RB. Principles and Practice of Structural Equation Modeling. Third edition. The Guilford Press. New York, USA, 2011.

Weiner et al. Psychometric assessment of three newly developed implementation outcome measures. Implementation Science. 2017; 12:108.

Statistical analysis plan part d) for the PASC Health Economic Impact (PASC-HEI)

Health economic evaluations of patient safety interventions in healthcare are limited, though previously we have evaluated the cost-effectiveness of the World Health Organization's Surgical Safety Checklist (Healey et al. 2022). It is vital to evaluate the impact of new patient safety interventions on costs and benefits for patients and society. Hence in the PASC trial we aim to investigate the health economic impact of the Patient Safety Checklist (PASC) in the PASC Stepped Wedge Cluster Randomized Controlled Trial ([name], 2017).

The main hypothesis is that the PASC is cost-effective for both patients and society. Primary outcome is costs associated with implementation of the PASC, where length of hospital stay is a major component for the overall treatment cost (Healey et al, 2022).

Statistical power of the PASC trial on PASC-HEI

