For the evaluation of implementation costs in combination with the clinical outcome data (i.e. complications and length of stay) the analysis builds on empirical data from the trial and our previous analysis methods published by Healey et al. (2022). In the cost-effectiveness analysis the mean difference in the absolute probability of the hospital admission is linked to a procedure being complication free, from control to intervention arms. We will investigate 30-days complication-free hospital admissions per 100 admissions. Ordinary least squares regression with a binary approach will be used to identify mean differences of the total costs per admission and the probability of hospital admissions without complications. A nonparametric approach will be used to estimate standard errors on mean cost effects with 95% confidence intervals.

We will estimate the cost impact of the PASC for a hospital bed-day equivalent and express the estimated cost difference as a "quality adjusted life year" (QALY). In Norway, the cost-effectiveness threshold is estimated by Woods et al (2016) to be between 43% and 93% of gross national income (GDP) per capita. We will present QALY equivalent effectiveness of the PASC as the lower, mid-point and upper-bound of this range (Healey et al, 2022).

Missing data on cost of hospital admissions and clinical covariates will be replaced with missing imputation (assumed missing at random) to reduce loss of power in the regression analysis (Azur et al, 2011). Missing data will be managed by creating 200 imputed datasets and the imputation model included all variables that to be included in adjusted regression model (Healey et al 2022). To test for sensitivity of the cost-effectiveness of the PASC implementation we use an upper and lower quartile excess bed-day cost from UK data to adjust for the Norwegian per diem costs (NHS, 2017).

The sample size calculation and the statistical analysis plan to be used on PASC-HEI was originally described in the 2.0 protocol, and updated 30th August 2024, by [name] [name], Department of Anaesthesia and Intensive Care, Haukeland University Hospital, Bergen, Norway; and Faculty of Health Sciences, Department of Nursing and Health Promotion, Acute and Critical Illness, Oslo Metropolitan University, Oslo, Norway.

References

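### Part d) of the SAP names no auxiliary variable for imputing missing admission cost; without length of stay the imputation adds nothing over complete cases for cost and can leave a bias

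*SAP*

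**What the plan says.** All of this is in part d) of the SAP (PASC Health Economic Impact) unless noted.

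- **What is imputed and why:** "Missing data on cost of hospital admissions and clinical covariates will be replaced with missing imputation (assumed missing at random) to reduce loss of power". One sentence covers both the cost outcome and the clinical covariates.
- **How:** "Missing data will be managed by creating 200 imputed datasets", and "the imputation model included all variables that to be included in adjusted regression model". Nothing else is said about the content of the imputation model. Part d) does not list the covariates of the cost regression.
- **The analysis model:** "Ordinary least squares regression with a binary approach will be used to identify mean differences of the total costs per admission", and likewise for the probability of a complication-free admission. Cost is therefore the dependent variable.
- **Length of stay:** in the introduction to part d), "length of hospital stay is a major component for the overall treatment cost". Elsewhere it appears only as an outcome. Part a), under Statistical analyses, separates the adjustment variables from the outcomes, and the outcomes end with "mortality up to 30 days after surgery, and length of hospital stay".

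**The concern.** An admission with a missing outcome and observed regressors carries no information about the regression of that outcome on those regressors. Filling the gap from the same regressors puts back what the complete cases already said, with random noise added. More imputed datasets reduce the noise but add no information. Only a variable outside the regression that predicts cost can do that. By the SAP's own description length of stay is the obvious candidate, and the stated rule does not bring it in.

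The same gap affects the missing-at-random assumption. If the imputation model holds only arm and case-mix, missingness must be unrelated to cost given those variables. If long stays are more often uncosted, that fails: the expensive tail is thinned and a real saving looks smaller. The mean cost difference feeds the QALY-equivalent figures in part d). The planned sensitivity analysis varies the bed-day unit cost and does not examine missingness.

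**Working it through.** **Inputs from the SAP.** Trial size 7 wards x 20 months x 38 patients = 5320 = 2 x 2660, which agrees with the stated totals; OLS on cost per admission; multiple imputation from the regression's variables. The SAP gives no missing-cost share, cost SD or expected cost difference, so everything below rests on assumed values.

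**Step 1: precision by formula.** Let m be the share of costs missing at random and r the correlation of cost with stay. The standard error relative to full data is:

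- without stay in the imputation model: sqrt(1/(1-m)). With m = 0.2, sqrt(1/0.8) = 1.118.
- with stay: sqrt(1 + (1-r²)m/(1-m)). With m = 0.2 and r = 0.9, sqrt(1 + 0.19 x 0.25) = 1.023. With r = 0.7, sqrt(1 + 0.51 x 0.25) = 1.062.

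**Step 2: simulation at the trial's size.** N = 5320, 150 replicates, OLS of cost on arm and two covariates, normal-model imputation with 40 datasets (fewer than the planned 200, for speed), pooled by Rubin's rules. Assumed: cost = 10 + 10 x stay + noise (SD 12); stay 0.5 day shorter under PASC, so a true difference near -5; stay always observed; clustering ignored. Each cell gives the mean estimate (mean standard error).

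| Cost missing | Full data | Complete cases | Imputed, regression variables | Imputed, plus stay |
|---|---|---|---|---|
| 20%, at random | -4.957 (0.746) | -4.985 (0.834) | -4.985 (0.833) | -4.958 (0.765) |
| 20%, log-odds +0.2 per day of stay | -5.009 (0.748) | -4.837 (0.759) | -4.837 (0.762) | -5.038 (0.767) |
| 22%, log-odds +0.4 per day of stay | -4.930 (0.748) | -4.441 (0.688) | -4.438 (0.687) | -4.916 (0.767) |

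- Imputation from the regression's variables matches complete cases in every row.
- Row 1, standard error against full data: 0.833/0.746 = 1.117 without stay and 0.765/0.746 = 1.025 with stay, in line with step 1.
- Row 2, shrinkage of the difference: 1 - 4.837/5.009 = 3.4%. Row 3: 1 - 4.438/4.930 = 10.0%. Adding stay removes it.
- In row 3 the standard error without stay (0.687) is below the full-data value (0.748), because the costly tail is missing. The standard error therefore gives no warning.

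**Step 3: missing covariates.** With cost complete and one covariate missing in 20%, imputing from the regression's variables gives a standard error of 0.750, against 0.837 for complete cases and 0.748 for full data. Here the SAP's stated purpose is met.

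**Step 4: a more skewed cost distribution.** Assumed: 20% of costs missing, log-normal stay (log-SD 0.8), cost correlated 0.93 with stay, stay 5-10% shorter under PASC. In runs with 1,000,000 and 4,000,000 admissions the complete-case saving was too small by:

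| Rise in log-odds of missing cost per SD of log stay | Understatement |
|---|---|
| 0.5 | 10-14% |
| 1.0 | 27-31% |
| 1.5 | 38-40% |

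With stay in the imputation model the bias was below 1%.

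**The case against.** - **The rule is a minimum.** A reader might infer that the SAP restricts the imputation to the regression's variables and shuts out length of stay. The text does not say that. It says all regression variables are included and excludes nothing. It also credits the approach to an earlier published evaluation that is not at hand. This stands. What remains is that the rule is the plan's only specification: an analyst who follows it need not include stay, and one who adds it makes an unplanned choice.
- **The power claim is partly right.** A reader might infer that the imputation recovers no power at all. Step 3 shows otherwise for the clinical covariates, which the same sentence covers. The point is confined to missing cost.
- **Complication status may already be in the model.** If one imputation serves both regressions, complication acts as an auxiliary for cost, and equality with complete cases no longer holds exactly. This stands, but the gain looks small. With complications assumed at 12.5% and log-odds 1.0 per SD of log stay, the step 4 bias fell only from 27% to 25% (slope 1.0) and from 38-40% to 36-37% (slope 1.5).
- **Cost may be derived from stay.** Part d) speaks of bed-day equivalents and per diem costs. If cost is largely stay times a unit price, stay may be missing whenever cost is, and naming it would then help little. This stands as a limit on the benefit.
- **Nothing shows that long stays are less often costed, or that missing cost is common.** This also stands, so the bias is conditional. In step 2 it is modest: 0.172 (5.009 - 4.837) and 0.492 (4.930 - 4.438), or about 0.2 and 0.6 of the standard error of 0.833.

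**Conclusion.** The point holds as a weakness in the specification of one work package. For admissions missing only cost, a model built from the regression's own variables gives the complete-case estimate and standard error, whatever the number of imputations, so the stated reduction in power loss is not achieved for cost. At an assumed 20% missing at random, that is about 12% excess standard error, against about 2-6% with stay included.

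The documents do not support saying that the cost result will be biased. There is no bias if missingness is unrelated to stay. If it rises with stay, the assumed scenarios give an understated saving of about 3-40%, and the upper end needs the steepest assumed slope. No scenario was run in which short stays are the ones left uncosted. These figures assume that stay is recorded where cost is not, and the step 2 simulation ignores clustering.

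**What to change.** In the missing-data paragraph of part d), replace the rule on the imputation model with wording such as: *The imputation model for admission cost contains all variables of the adjusted cost and complication regressions, including trial arm, and in addition length of stay and complication, readmission and death within 30 days, where recorded. Cost is imputed by predictive mean matching; the OLS analysis stays on the raw cost scale. The complete-case result is reported alongside.*

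Predictive mean matching handles skewed cost without leaving the raw scale. Imputing on the log scale fits less well with an OLS analysis of raw mean cost.

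The cost is a short change to the text and a slightly longer imputation model. The added variables are outcomes that part a) already lists, so no further data or patients are needed. The benefit is limited to admissions where stay is recorded but cost is not.

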d. Effect size measured by the root-mean-square standardized effect.

Statistical analysis

Descriptive statistics (i.e. frequencies, percentages, mean, standard deviations) will be used to assess responding patients' characteristics, clinical variables, and surgical specialties (i.e. comorbidity, type of anesthesia or surgery, length of surgery) and EQ-5D-3L dimensions. To investigate the PASC intervention effect on EQ-5D-3L, a chi-squared test will be used to test any differences on patient characteristics between the trial arms. General Linear model with analysis of covariance will be used to investigate mean score difference between control and intervention arms. If there are significant variations in patients' characteristics and clinical variables between the two arms adjustments for these differences will be applied in the regression model to compare effects across the domains (Jansson, 2011). All analysis will be performed in SPSS 29.0 (IBM Corp, Armonk, NY) and a two-sided P value at 0.05 will be considered statistically significant.

The validity and reliability of the EQ-5D-3L will be investigated. The internal consistency will be measured by using Cronbach's alpha (scores between 0 and 1, preferably >0.7) and Pearsons' correlation or Spearman's rho as appropriate. Psychometric evaluation will be performed by measuring the hypothesized structure model of the EQ-5D-3L with fit indicators as χ^2 , CFI, TLI, and RMSEA (Bollen 1989, Kline 2011). The analysis will be performed in IBM SPSS version 29 and IBM SPSS AMOS version 26.

According to Kline (2011, p. 225) the sample size required to perform Structured Equational Modelling (SEM) usually requires 3-400 cases for models when degrees of freedom are <10. With higher degrees of freedom, i.e. > 20, a smaller number of cases is required for a minimum power of 0.80. However, the sample size should never be less than 100 in any event (Kline, 2011). The degrees of freedom within EQ-5D-3L, including 7 surgical clusters are anticipated to exceed this number on degrees of freedom. Accordingly, in all, more than 200 cases (respondents) are sufficient sample for conducting SEM (confirmatory factor analysis) with the EQ-5D-3L data. Missing data will be managed by creating 200 imputed datasets and the imputation model included all variables that to be included in adjusted regression model.

The sample size calculation and the statistical analysis plan to be used on EQ-5D-3L data were described in protocol version 2.0 (30th June 2021), along with the description of statistical analysis of the HLQ survey, and updated 30th August 2024, by [name] [name], Department of Anaesthesia and Intensive Care, Haukeland University Hospital, Bergen, Norway; and Faculty of Health Sciences, Department of Nursing and Health Promotion, Acute and Critical Illness, Oslo Metropolitan University, Oslo, Norway.

References

- Bollen K. Structural equations with latent variables. Wiley-Interscience publication. Mexico. 1989. ISBN 0-471-01171-1.
- Jansson K-Å, Granath F. Health-related quality of life (EQ-5D) before and after orthopedic surgery. *Acta Orthopaedica* 2011; 82(1):82-89.
- Kline RB. Principles and Practice of Structural Equation Modeling. Third edition. The Guilford Press. New York, USA, 2011.

Statistical analysis plan f) for PASC impact on patients' health literacy

The main hypothesis is that PASC improve surgical patients' health literacy. The primary outcome is the nine dimensions in the Health Literacy Questionnaire (HLQ), developed by Osborn et al 2013).

Statistical power and sample size required for HLQ in the PASC trial

A power analysis was performed to assess the required number of participants in the survey. It was based on mean score results in a previous Norwegian study of health literacy in a population of patients with skin diseases (Wahl, 2021). The lowest number of individuals required to detect a clinical meaningful mean score difference at 0.30 between the baseline and intervention groups would be $n = 103$ patients in each arm of the PASC trial. A standard deviation at 0.66 in both arms were assumed. Power was estimated at 90% and a type I error at 0.05. Previous research experiences on surveys in Norwegian hospitals indicate that patients' responses could possibly be 35% (Boge, 2019). Hence, we include 50 patients per cluster with a total of 350 patients in the baseline group and 350 patients in the intervention group to ensure enough respondents.

The survey instrument

The HLQ consists of 44 questions with 9 domains that represent patients' health literacy. The domains are labelled as 1: Understood and supported by health professionals. 2: Satisfactory information to handle own health. 3: Active management of own health. 4: Social support of own health. 5: Consider health information. 6: Active cooperation with health professionals. 7: Navigation through the healthcare system. 8: Possibilities to find right health information and 9: Understand the health information to be able to know what should be done.

Statistical analysis

Descriptive statistics (i.e. frequencies, percentages, mean, standard deviations) will be used to assess patients' characteristics (i.e. age, gender, comorbidity, educational level, societal status). To investigate the PASC intervention effect on health literacy, a chi-squared test will be used to test any differences between the trial arms. General Linear Model will be used to investigate mean score difference between control and intervention arms. If there are significant variation in patients' characteristics between the two arms a linear regression model will be applied to adjust for it and to compare effects across the nine domains on health literacy (Osborne, 2013).

All analysis will be performed in SPSS 29.0 (IBM Corp, Armonk, NY) and a two-sided P value at 0.05 will be considered statistically significant.

Validity and reliability of the HLQ will be investigated. The internal consistency will be measured by using Cronbach's alpha (scores between 0 and 1, preferably >0.7) and Spearman's rho for correlations between the dimensions. Psychometric evaluation will be performed by measuring the hypothesized structure model of the HLQ with fit indicators as χ^2 , CFI, TLI, and RMSEA (Bollen 1989, Kline 2011). This analysis will be performed in IBM SPSS version 29 and IBM SPSS AMOS version 26.

According to Kline (2011, p. 225) the sample size required to perform Structured Equational Modelling (SEM) usually requires 3-400 cases for models when degrees of freedom are <10. With higher degrees of freedom, i.e. > 20, a smaller number of cases is required for a minimum power of 0.80. However, the sample size should never be less than 100 in any event (Kline, 2011). The degrees of freedom within PASC-EQ/PASC-IQ data, including 7 surgical clusters, are 32. Accordingly, more than 200 cases (respondents) are sufficient sample for conducting SEM (confirmatory factor analysis) with PASC-EQ/PASC-IQ data. Missing data will be managed by creating 200 imputed datasets and the imputation model included all variables that to be included in adjusted regression model.

The sample size calculation and the statistical analysis plan to be used on HLQ data were described in protocol version 2.0. The SAP was up-dated 30th August 2024. The original statistical plan and the update was made by [name] [name], Department of Anaesthesia and Intensive Care, Haukeland University Hospital, Bergen, Norway; and Faculty of Health Sciences, Department of Nursing and Health Promotion, Acute and Critical Illness, Oslo Metropolitan University, Oslo, Norway.

References

- Boge RM, [name], [name] RM, Bruvik F, Harthug S. Discharge care quality in hospitalised elderly patients: Extended validation of the Discharge Care Experiences Survey. *Plos One*. 2019, 14(9):e0223150.
- Bollen K. Structural equations with latent variables. Wiley-Interscience publication. Mexico. 1989. ISBN 0-471-01171-1.
- Osborne RH, et al. The grounded psychometric development and initial validation of the Health Literacy Questionnaire (HLQ). *BMJ Public Health* 2013;13(658).
- Wahl AK, Hermansen Å, Osborne RH, Larsen MH. A validation study of the Norwegian version of the Health Literacy Questionnaire: a robust nine-dimension factor model, *Scand. J. Public Health*. 2021, 49(4):471-478.
- Kline RB. Principles and Practice of Structural Equation Modeling. Third edition. The Guilford Press. New York, USA, 2011.

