Statistical Analysis Plan for the Patient Safety Checklist (PASC) Stepped Wedge Cluster Randomized Controlled Trial.

The original protocol version, including description of the statistical analysis, was approved by the Regional Ethical Committee of Western Norway (REK west) on the 21st of September 2016. The statistical analysis plan was drafted by [name] [name] (head of project) and Professor in biostatistician [name], who also performed sample size calculations for the trial (expected $n = 4200$ in original protocol version 1.0). The approval was signed by the committee chair, [name] (reference 2016/1102/REK vest). The English title was “Effects on patient outcome in surgery: Development and Implementation of Patient Safety Checklists (PASC) before, during and after in-hospital surgery – a cluster RCT” with reference number 2016-1102.

The 1.0 protocol version was updated to version 2.0 on 30th of June 2021, and to version 2.1 on 10th of August 2022. The updates were approved by REC west, and they were signed by the committee chair, [name] and by senior consultant [name] (references 20569). The sample size calculation was updated in version 2.0 (30th of June 2021) prior to start of PASC data collection (1st of November 2021). The calculation was performed by Professor in biostatistics, [name] and yielded then a required sample size at 5320 (protocol version 2.0). This update was based on empirical data from the development and validation of the PASC the intervention (Harris et al, 2022).

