The primary hypothesis is that PASC reduce complications up to 30 days after surgery. Secondary hypotheses are that PASC reduce readmissions to hospital, length of hospital stay, and mortality up to 30 days after surgery.

Complications are in this trial observations of the surgical complications registered in patients' medical records and coded according to the International Classification of Diseases – 10th version (ICD-10) by surgeons or ward doctors. One or more complications per hospital stay per patient will be given the values zero or one, as the main outcome variable. Similarly, secondary outcomes. i.e. mortality, will be given zero or one (for events).

Statistical power

In protocol version 1.0, the sample size was calculated to be 4200 cases across the clusters. Based on data from a pilot of PASC feasibility (Harris et al, 2023), an update was required. The sample size analysis was updated in protocol 2.0 (30th June 2021):

The pooled overall proportion of surgery-related complications (i.e. infections, bleedings, cardiac or lung related) has previously been estimated to be 15% and is the primary outcome for the present analysis (Storesund et al, 2020). We propose that the inclusion of PASC will lower this proportion by at least 5% (corresponding to a 33.3% relative risk reduction). Using the stepped wedge power analyses command in Stata (*steppedwedge* command), we calculated that the lowest number of individuals required to detect the 5% reduction is 5320. The calculation was carried out using a non-standard stepped wedge design (see diagram below): 7 wards x 20 months x 38 patients (on average). We further assumed that the intra-cluster correlation (ICC) was 0.05 and that the type I error and type II error were 0.05 and 0.20, respectively.

Statistical analyses

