Statistical analysis plan b) on the PASC checklist on patients self-screening on their risk of malnutrition prior to surgery.

The main hypothesis is that PASC reduce the risk of nutritional events after surgery. Nutritional complications are a primary outcome based on ICD-10 codes, and secondary outcome are comparison of patients and healthcare staffs' risk assessments by comparing use of the Malnutrition Screening Tool (MST) (Ferguson et al, 1999). Three MST items are scored from 0-7, where a total sum score at 2 and above, represents patients being at risk of malnutrition. Secondary hypothesis is that patients can screen themselves of the malnutrition risks and just as well as the healthcare staffs' screening of the patients' malnutrition risks.

Descriptive analysis with frequencies, percentages, means, and standard deviations will be applied. A chi-squared test will be applied to detect differences in patient characteristics and clinical variables from baseline to intervention steps. A logistic regression model will be used to adjust for any variations in characteristics or clinical variables between control and intervention steps. Validity of the Malnutrition Screening Tool will be investigated with nutrition parameters of the scale and objective variables (ICD-10 codes). Agreement between patients' ratings and healthcare staffs' ratings on the malnutrition risk scale will be measured with percentages, Kappa and intraclass correlation (ICC) with absolute agreement as appropriate. Correlations will be performed with Pearsons' correlation or Spearman's rho, as appropriate.

Missing data will be managed by creating 200 imputed datasets and the imputation model included all variables to be included in adjusted regression model. Statistical analyses will be performed by Stata and in SPSS. All P-values are two sided and values $P < 0.05$ are considered statistically significant.

The statistical analysis plan was described in the protocol 1.0, 2.0 and 2.1, and further detailed here, by [name] [name].

Reference

Ferguson M, et al. Development of a Valid and Reliable Malnutrition Screening Tool for adult Acute Hospital Patients. *Applied Nutritional Investigation*. 1999; 15(6):458-464.

Statistical analysis plan for parts of both a) and c)

Statistical analysis plan for the Patient Safety Checklist Experience Questionnaire (PASC-EQ) and the PASC Implementation Questionnaire (PASC-IQ)

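### The nutrition, cost, EQ-5D-3L and HLQ comparisons have no calendar-time term and no stated ward term, so part of any secular trend is credited to PASC

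*SAP*

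**What the plan says.** The title gives the design: "Statistical Analysis Plan for the Patient Safety Checklist (PASC) Stepped Wedge Cluster Randomized Controlled Trial".

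- **Plan a), Statistical analyses:** "To account for potential temporal trends in the outcome, we will include calendar month as a continuous (linear or nonlinear) term in all models". There is also a random intercept for hospital. The outcomes listed there are complications, readmission, mortality and length of stay.
- **Plan b), nutrition:** "A logistic regression model will be used to adjust for any variations in characteristics or clinical variables between control and intervention steps".
- **Plan d), survey:** a chi-squared or t-test between arms, then a general linear model if patient characteristics differ significantly.
- **Plan d), cost-effectiveness:** "Ordinary least squares regression with a binary approach will be used to identify mean differences of the total costs per admission", and likewise for the probability of an admission without complications. The covariates are not listed. Standard errors for mean cost effects come from a nonparametric method whose resampling unit is not given.
- **EQ-5D-3L:** "General Linear model with analysis of covariance will be used to investigate mean score difference between control and intervention arms", with adjustment for patient and clinical variables that differ significantly.
- **HLQ:** a chi-squared test between arms, and "General Linear Model will be used to investigate mean score difference between control and intervention arms", with adjustment for patient characteristics that differ significantly.

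None of these four parts names calendar time or a ward effect, and none refers back to the model in plan a). Where they mention the seven clusters, it is for sampling numbers or for degrees of freedom in the factor models.

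**The concern.** In a stepped wedge the exposed share rises with time, so exposure and calendar time are confounded by design. The staggered, randomised order of wards lets the two be separated, but only if time is in the model. Without it, each comparison is close to a before-after study: drift in coding practice, length of stay or patient mix between the earlier and later part of the trial is partly read as an effect of PASC. Adjusting for patient and clinical characteristics that happen to differ does not bring calendar month in. Four work packages have primary outcomes analysed this way.

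**Working it through.** **1. The plan's own power figures.** Inputs from the EQ-5D-3L section: means 0.5 and 0.6, SD 0.3, two-sided alpha 0.05.

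- 200 + 200: SE = 0.3 × √(1/200 + 1/200) = 0.030. Power ≈ Φ(0.1/0.030 − 1.96) = 0.915; noncentral t gives 0.914, as stated.
- 125 + 200: SE = 0.3 × √(1/125 + 1/200) = 0.0342. Power ≈ Φ(2.92 − 1.96) = 0.832; noncentral t gives 0.830, as stated.
- HLQ (difference 0.30, SD 0.66, power 90%): the normal formula gives 102 per arm, and 103 per arm gives power 0.901 by noncentral t, in line with the stated 103.

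All three reproduce as comparisons of two independent groups, with no ward or time term.

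**2. The time gap between arms.** Plan a) gives 7 wards, 20 months and 38 patients on average per ward and month (7 × 20 × 38 = 5320). The diagram is not shown, so an even rollout is assumed, with wards having 2, 5, 8, 10, 12, 15 and 18 control months (70 of 140 ward-months).

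- Sampling spread evenly over ward-months: mean control month = 478/70 = 6.83; mean intervention month = 992/70 = 14.17. Gap = 7.34 months. Share of a linear drift from month 1 to 20 = 7.34/19 = 39%.
- Equal numbers per ward and arm, spread over each period: with c control months, the ward means are (c + 1)/2 and (c + 21)/2, so the gap is 10 months in every ward. Share = 10/19 = 53%.
- If the trial spans 27 months (plan a) codes month of surgery 1 to 27), the gaps are about 10.0 and 13.5 months, and the shares 10.0/26 = 39% and 13.5/26 = 52%.

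**3. Size of the false effect.** Bias = total drift × share. The drifts below are assumptions; the SAP gives none.

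| Assumed EQ-5D-3L drift over the trial | False effect (39% to 53%) |
|---|---|
| 0.03 | 0.012 to 0.016 |
| 0.05 | 0.020 to 0.027 |
| 0.10 | 0.039 to 0.053 |

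Simulation (2000 runs per scenario, 125 + 200 patients, SD 0.3, no true effect) agrees. At drift 0.10 the arm-only model gave false effects of 0.038 to 0.053 and rejected in 19 to 33% of runs against a nominal 5%.

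**4. Ward.** With no drift and a ward ICC of 0.05 (plan a)'s value, borrowed for EQ-5D-3L), the arm-only model rejected in 11% of runs when sampling followed ward-months and in 5% when it was balanced by ward.

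**5. With ward and linear month in the model.** Bias is near zero and rejection under the null is 4 to 6%. At ICC 0.05 the SE rises from 0.034 to 0.058–0.061. Power for 0.1 is then about Φ(0.1/0.058 − 1.96) = 0.41 to Φ(0.1/0.061 − 1.96) = 0.37; simulation gave 0.43 and 0.38.

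**The case against.** - **Plan a) says all models.** The phrase could be read trial-wide. But it stands in plan a)'s paragraph on complications, followed by that plan's variables and outcomes, and the later sections set out different models without reference to it. If trial-wide use was meant, one sentence in each section settles it.
- **Adjustment is broader than demographics.** Plans b) and EQ-5D-3L allow clinical variables, and type of surgery may partly stand in for ward. In d) the covariates are unlisted, and the method builds on an earlier publication that cannot be checked here. This stands, so for d) one can say only that no such term is stated. None of it supplies calendar time.
- **The magnitude depends on sampling dates.** This stands. HLQ takes 50 patients per ward and arm. At 38 per ward and month that is 50/38 = 1.3 months of accrual. If drawn just before and just after crossover, the gap is about 1.3 months and the share 1.3/19 = 7%. Sampling at the extremes would widen the gap.
- **Ward matters less than time.** This stands where sampling is 50 per ward and arm. Leaving ward out then mainly affects the SE, and biases the estimate only if response differs by ward.
- **Implementation costs have no control-period trend.** This stands. Meetings, printing and distribution arise only under the intervention. Within d), the length-of-stay and complication-free components are the ones affected.

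**Conclusion.** The point holds. As written, b), d), EQ-5D-3L and HLQ specify control-versus-intervention comparisons with no calendar-time term and no stated ward term, in a design where time and exposure move together. Under an even 20-month rollout with sampling spread over each period, about 39 to 53% of a linear drift is credited to PASC. The rollout, drift sizes and ward ICC for EQ-5D-3L are assumptions; the direction of the problem follows from the design.

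A reader might infer more than the document supports:

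- That the whole of any trend becomes a PASC effect. Only part does, and little if survey patients were drawn near crossover.
- That every trial patient enters these comparisons. The survey outcomes use samples or respondents.
- That all standard errors are too small for want of a ward term. Ward-balanced sampling does not have that consequence, and the resampling unit for costs is unknown.
- That the trial's main result is affected. Complications have a month term in plan a); the outcomes here are primary only within their own work packages.

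The stated EQ-5D-3L power of 0.83 holds only for an analysis that ignores the design.

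**What to change.** State in b), d), EQ-5D-3L and HLQ that every effect estimate comes from a model with an intervention indicator, a calendar-month term and a ward effect. Name ward explicitly, because plan a)'s random intercept is for hospital. With seven wards, use fixed ward effects, or a random effect with a small-sample correction. This means logistic models for nutritional events and linear models for EQ-5D-3L, HLQ and costs.

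In d), list the covariates and make the nonparametric standard error respect ward. Do not use the unadjusted between-arm tests in the d) survey and the HLQ section as tests of effect. The chi-squared comparisons of patient characteristics, as in b) and EQ-5D-3L, may stay. State when survey patients were sampled relative to each ward's crossover.

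No new data should be needed: month of surgery is a listed variable and ward is the sampling unit. The cost is precision. EQ-5D-3L power for a difference of 0.1 drops from 0.83 to about 0.4 under the assumed rollout. The EQ-5D-3L and HLQ power statements should be recalculated for the actual rollout and the adjusted model, and the loss disclosed.
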